12.8.3 Procedure for withdrawal

The date and reason for withdrawal of a subject or the premature termination of the study must be documented in the eCRF.

After withdrawal of a subject, all AEs or complications should be followed for as long as the Investigator considers it necessary.

Subjects who have received at least one dose of study drug should as far as possible be followed for safety according to the protocol. Blood and nasal sampling for immunology parameters will not be performed.

Subjects who have received one dose of study drug and are diagnosed with laboratory-confirmed influenza prior to the second dose should not receive a second vaccination but should, as far as possible, be followed for safety according to the protocol. Blood and nasal sampling for immunology parameters will not be performed.

Subjects who withdraw before receiving any IMP should not participate in any further study related procedures.

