12.8.4 Replacement of withdrawn subjects

Randomised subjects will not be replaced.

Subjects who develop suspected influenza during the study period should be tested using a diagnostic test at the discretion of the Investigator (Section 15.10). If influenza is confirmed no further treatment with study drug should be given. Safety should as far as possible be followed according to the protocol excluding further sampling for immune parameters. Subjects diagnosed with influenza before receiving any study drug should not participate in any further study related procedures.

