14.1 STUDY VISITS

14.1.1 Visit 1, Screening

After written informed consent has been obtained, the following activities and assessments will be performed:

- Evaluation of eligibility criteria.
- Collection of demographic data.
- Recording of medical history.
- Physical examination.
- Recording of vital signs (heart rate and blood pressure).
- Recording of weight and height.
- 12-lead ECG.
- Pregnancy test, urine dipstick.
- Blood sample for viral screen (HIV, hepatitis B and hepatitis C).
- Urine drug screen (dipstick).
- Urine sampling for assessment of urinalysis parameters.
- Blood sampling for assessment of haematology and clinical chemistry parameters. Fasting is not required.
- Nasal swab for nasal IgA analysis (pre-treatment sample, to be stored and analysed with the other immune samples. Performed at screening to save time at visit 2 especially for group 1 to 4).
- Recording of prior and concomitant medication.

Eligible subjects will be scheduled for Visit 2.

14.1.2 Visit 2

Subjects will arrive at the study clinic on Day 0. A re-assessment of eligibility will be made, see Section 12.6. Eligible subjects will be randomised to one of 6 treatment groups as detailed in Section 11 and 13.1.

The activities and assessments to be performed at Visit 2 are outlined below. For details on the timing of each assessment, refer to Table 2 (group 1 to 4) and Table 4 (group 5 and 6).

The following activities and assessments will be performed **before randomisation**:

- Pregnancy test (urine dipstick).
- Recording of vital signs (heart rate, blood pressure and body temperature).
- Recording of concomitant medication.
- Collection of pre-dose events.

The following activities and assessments will be performed **after randomisation** but **pre-dose**:

- Blood sampling for immunology analyses.

- Inspection of nasal cavities and recording of local tolerability parameters (group 1 to 4 and group 6).
- Inspection of administration site (upper arm) and recording of local tolerability parameters (group 5).

The **study drug administration** will be performed as summarized in Section 13.5.1 and Section 13.5.2 and according to the manufacturers' instructions as applicable.

The following activities and assessments will be performed **post-dose**:

- Recording of local tolerability parameters at 15 and 120 minutes post study drug administration.

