18.4.1 Full Analysis set

The full analysis set (FAS) is used to describe the analysis set that is as complete as possible and as close as possible to the intention-to-treat (ITT). The FAS will consist of all randomised subjects who received at least one dose of study medication and have at least one post-randomisation efficacy assessment.

The FAS analysis will be the primary analysis for evaluation of immune response and immunology efficacy data and will be performed for all efficacy endpoints unless otherwise stated. Subjects will be analysed according to the treatment group to which they were randomised.

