18.4.2 Per-protocol Analysis Set

The per-protocol analysis set (PPAS) is a subset of the FAS and consists of all subjects without any major protocol deviations, i.e. a set of subjects that participated in the study as intended.

Analysis based on the PPAS will be used to assess the robustness of the results from the FAS analyses. Subjects will be analysed according to treatment which they received.

Subjects diagnosed with influenza after start of treatment will not be included in the PPAS.

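### Immunology sampling stops after withdrawal or confirmed influenza, so the last post-dose titres in the FAS come only from subjects without these events, and the PPAS cannot show what that does to the results

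*Combined protocol and SAP*

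**What the plan says.** Section 12.8.3 deals with subjects who are withdrawn after at least one dose and, separately, with subjects whose influenza is confirmed before the second dose. Both are to be followed for safety where possible. In both cases "Blood and nasal sampling for immunology parameters will not be performed". Section 12.8.4 extends this to influenza confirmed at any point: "Safety should as far as possible be followed according to the protocol excluding further sampling for immune parameters". Testing is for suspected cases, who "should be tested using a diagnostic test at the discretion of the Investigator". The same section adds that "Randomised subjects will not be replaced".

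Section 18.4.1 makes the FAS primary for immune response and describes it as "as complete as possible and as close as possible to the intention-to-treat (ITT". Its members are "all randomised subjects who received at least one dose of study medication and have at least one post-randomisation efficacy assessment", grouped as randomised. Section 18.4.2 defines the PPAS as a subset of the FAS without major deviations, grouped by treatment received, and gives it the role of robustness check. It adds that "Subjects diagnosed with influenza after start of treatment will not be included in the PPAS".

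Section 18.5.3.1 specifies an ANCOVA with baseline, treatment and site, calls the comparisons exploratory, and gives no rule for missing titres. Section 18.1 leaves further detail to a separate SAP, whose text is not in the document at hand.

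**The concern.** An analysis set can be close to ITT only if outcomes are still collected after subjects leave the intended course. Here collection is stopped by rule, in people who may still be coming to the clinic. A later SAP can choose how to handle missing values, but it cannot recover samples that were never taken.

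What is at stake is the comparison of Endocine groups with antigen alone and saline at Day 42, the time point after the second dose. Section 18.2 calls the effect of Endocine a key objective. Loss could plausibly differ by group. Section 9.5 reports more local symptoms with Endocine, slightly more at 2%, and Section 12.8.1 lists adverse events among the reasons for discontinuing a subject. Section 9.6 says vaccination may protect in the coming season, which saline cannot do. If loss differs by group and the lost subjects respond differently, the contrast is biased, and the one robustness check named would not show it.

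**Working it through.** **Group sizes.** The plan randomises 162 subjects in the ratio 2:2:2:1:1:1. 162 × 2/9 = 36 and 162 × 1/9 = 18; 3 × 36 + 3 × 18 = 162. The stated sizes are reproduced. Section 18.2 disclaims a power calculation and states no dropout rate, so there is no planned loss to compare with.

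**Tracing subjects through the rules.** I read a post-randomisation efficacy assessment as a post-dose one. Read literally, the Visit 2 blood sample would also count, since Section 14.1.2 lists it among activities "performed after randomisation but pre-dose". Groups 1 to 4 give their Visit 3 immunology samples before the second dose (Section 14.1.3.1).

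| Subject | In FAS | Day 21 titre | Day 42 titre (groups 1–4) | In PPAS |
|---|---|---|---|---|
| Completes, no major deviation | yes | yes | yes | yes |
| Withdrawn, or influenza, before the Visit 3 sample | no | no | no | no |
| Groups 1–4, withdrawn after the Visit 3 sample | yes | yes | no | depends on the major-deviation decision |
| Groups 1–4, influenza after the Visit 3 sample | yes | yes | no | no |
| Completes, with a major deviation | yes | yes | yes | no |

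The Day 42 column is filled only for subjects with neither event. Groups 5 and 6 have one post-dose sample, so the same holds for their whole post-dose analysis. At Day 42 the two sets differ in membership only by subjects with major deviations, because the influenza cases removed from the PPAS have no Day 42 titre in the FAS either. At Day 21 the PPAS can still remove influenza cases diagnosed after that sample.

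**Size for percentages.** Assume k of n subjects are lost: 2 to 4 of 36, or 1 to 2 of 18. If x of the n − k observed subjects respond, the full-group rate lies between x/n and (x + k)/n, a width of k/n.
- 2/36 = 1/18 = 5.6 points
- 4/36 = 2/18 = 11.1 points

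Example: with 17 of 34 observed responders and 2 lost, the full rate lies between 17/36 = 47.2% and 19/36 = 52.8%.

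**Size for GMT.** If lost subjects differ from kept subjects by g on the log2 scale, the kept mean differs from the full mean by (k/n) × g, so the GMT is off by a factor of 2^((k/n) × g).

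| Assumed gap g (log2) | k/n = 5.6% | k/n = 11.1% |
|---|---|---|
| 0.5 | 1.02 | 1.04 |
| 1 | 1.04 | 1.08 |
| 2 (4-fold) | 1.08 | 1.17 |

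A between-group ratio shifts by the ratio of the two groups' factors, so equal loss with equal gaps cancels. Only differential loss, or a different gap by group, biases the contrast.

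**The case against.** The strongest defence is that stopping samples after influenza is deliberate. Infection itself can raise HI and VN titres, so a vaccine-response question is better answered without them. This stands. With an assumed 16-fold gap (4 log2), putting post-infection titres into the primary FAS would move a group GMT by 2^(0.056 × 4) = 1.17 to 2^(0.111 × 4) = 1.36. If influenza were commoner on saline, it would shrink the contrast. But the plan does not say that this is its target, and the argument does not cover subjects withdrawn for other reasons.

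Four stronger readings are tempting, and the documents do not support them.
- *The FAS is really a completer set.* It requires one dose and one assessment, not completion. Groups 1 to 4 subjects lost after the Visit 3 sample stay in it with Day 21 data.
- *Missing the second dose ends sampling.* Section 12.8.3 covers withdrawal of a subject and influenza. Section 12.8 names discontinuation of treatment in its title but gives no separate path for a subject who stops dosing and stays in the study.
- *The PPAS is useless as a check.* It still tests major deviations, grouping by treatment received and, at Day 21, removal of influenza cases.
- *Loss is related to treatment.* This is plausible only. Section 9.5 also calls the local symptoms rapidly reversible, and Section 9.6 places vaccination before the expected outbreak. The clinic phase in these healthy adults lasts about six to seven weeks.

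It also stands that some withdrawn subjects (consent withdrawn, lost to follow-up, death) leave nothing to collect, so the recoverable share is smaller than the total loss.

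**Conclusion.** The concern holds in limited form. By rule, no titre exists after withdrawal or confirmed influenza. Day 42 in groups 1 to 4 and Day 21 in groups 5 and 6 are therefore analyses of subjects without these events, short of the stated FAS aim. The PPAS cannot test sensitivity to these missing values.

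The size rests wholly on assumed loss of 5.6 to 11.1% and assumed gaps of 0.5 to 2 log2. It is at most 5.6 to 11.1 points on a group's seroprotection or seroconversion rate, and a GMT factor of about 1.02 to 1.17. The percentage figures are extreme bounds, not expected bias.

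Consequences are modest: immunology is a secondary objective, the comparisons are declared exploratory, and safety follow-up is kept. This is a worthwhile improvement rather than a flaw that invalidates the design.

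**What to change.** - **Section 12.8.3:** for dosed subjects withdrawn for reasons other than influenza, keep the immunology blood and nasal samples already scheduled at Visit 3 and, in groups 1 to 4, Visit 4, provided the subject still attends for safety and consents to sampling.
- **Section 18.4.1:** analyse these samples in the FAS by randomised group.
- **Sections 12.8.4 and 18.4.1:** state that, for confirmed influenza, the FAS targets the response without infection. If samples are taken after influenza, use them only in a sensitivity analysis and not in the primary FAS analysis. The PPAS exclusion can stay.

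**Cost.** Protocol wording and a few extra tubes, swabs and assays. The final clinic visit already includes a blood draw for haematology and chemistry (Sections 14.1.3.2 and 14.1.4). At Visit 3 in groups 1 to 4 no safety bloods are scheduled, so the immunology draw there would be a separate one for a withdrawn subject.

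**Downside.** Some Day 42 titres will come from subjects who had only one dose. Analysis by randomised group accepts this, but it should be said in the report.

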12.8.4 Replacement of withdrawn subjects

Randomised subjects will not be replaced.

Subjects who develop suspected influenza during the study period should be tested using a diagnostic test at the discretion of the Investigator (Section 15.10). If influenza is confirmed no further treatment with study drug should be given. Safety should as far as possible be followed according to the protocol excluding further sampling for immune parameters. Subjects diagnosed with influenza before receiving any study drug should not participate in any further study related procedures.

13. STUDY TREATMENTS

13.1 TREATMENT GROUPS

Subjects in the study will be randomised to one of 6 treatment groups in a 2:2:2:1:1:1 ratio as outlined in Table 5. For details on each study drug, refer to Section 13.2. For details on treatment procedures, see Section 13.5.

13.2 IDENTITY OF THE INVESTIGATIONAL MEDICINAL PRODUCTS

13.2.1 TEST PRODUCTS

13.2.1.1 Immunose FLU (group 1 and 2)

Immunose FLU consists of influenza antigens (4 split inactivated virus suspensions; 15 µg HA/strain/0.3 mL) and Endocine in concentrations of 1% (group 1) or 2% (group 2). The influenza strains are the ones recommended by WHO for QIV for the northern hemisphere for season 2016/2017.

Endocine is composed of lipids (monoolein and oleic acid) that are formulated into liposomes.

Immunose FLU is a homogeneous, slightly turbid to turbid liquid and will be provided as 0.4 mL dispensed in 3 mL, flat bottomed, amber glass vials with white polypropylene screw caps.

13.2.1.2 Influenza antigen (group 3)

The influenza antigen consists of the same influenza antigens (4 split inactivated virus suspensions; 15 µg HA/strain/0.3 mL) as Immunose FLU.

The influenza antigen is a homogeneous, slightly turbid to turbid liquid and will be provided as 0.4 mL dispensed in 3 mL, flat bottomed, amber glass vials with white polypropylene screw caps.

13.2.1.3 Saline (NaCl) (group 4)

The saline solution will be provided as 0.4 mL in 3 mL, flat bottomed, amber glass vials with white polypropylene screw caps.

The solution is clear and colourless.

13.2.2 COMPARATORS**13.2.2.1 [REDACTED] (group 5)**

[REDACTED] contain the influenza strains as recommended by the WHO for [REDACTED] the northern hemisphere for the 2016/2017 season.

13.2.2.2 [REDACTED] (group 6)

[REDACTED] influenza virus strains as recommended by the WHO for [REDACTED] the Northern hemisphere for the 2016/2017 season.

Table 5 Treatment groups

Group	Subjects (n)	Test product/comparator	Antigen dose	Antigen type	Number of strains	Adjuvant (Endocine)	Route	Doses (n)	Volume (µl)	Storage
1	36	Immunose FLU (1 %)	15 µg HA/strain	Inactivated split virus	4	1%	intranasal	2	300	Refrigerator, 2-8°C
2	36	Immunose FLU (2 %)	15 µg HA/strain	Inactivated split virus	4	2%	intranasal	2	300	Refrigerator, 2-8°C
3	36	Influenza antigen	15 µg HA/strain	Inactivated split virus	4	-	intranasal	2	300	Refrigerator, 2-8°C
4	18	Saline (NaCl)	-	-	-	-	intranasal	2	300	Refrigerator, 2-8°C
5	18	[REDACTED]	[REDACTED]	[REDACTED]	[REDACTED]	[REDACTED]	[REDACTED]	1	[REDACTED]	Refrigerator, 2-8°C Light sensitive
6	18	[REDACTED]	[REDACTED]	[REDACTED]	[REDACTED]	[REDACTED]	[REDACTED]	1	[REDACTED]	Refrigerator, 2-8°C Light sensitive

13.3 MANUFACTURING, PACKAGING AND LABELLING OF INVESTIGATIONAL MEDICINAL PRODUCTS

Immunose FLU and the influenza antigen for nasal administration will be manufactured, packed and labelled by [REDACTED].

Saline will be packed and labelled by [REDACTED].

[REDACTED] will be manufactured by [REDACTED] and packed and labelled by [REDACTED].

[REDACTED] will be manufactured by [REDACTED] and packed and labelled by [REDACTED].

The test products will be provided in labelled boxes containing IMP for 2 dose administrations. The comparators will be provided in labelled boxes with IMP for 1 dose administration.

All IMP will be shipped to the pharmacy, Akademiska hospital (Uppsala, Sweden) before distribution to each site.

The labels on the boxes and IMP containers will include all information required by applicable regulations.

13.4 STORAGE AND HANDLING OF INVESTIGATIONAL MEDICINAL PRODUCTS

All IMPs and comparators should be stored in a safe place with limited access at 2 to 8°C. Temperature logs should be kept for the refrigerator where the IMP is stored. The temperature should be noted on a daily basis (working days only unless automatic temperature readings are available). The IMPs must not be frozen.

[REDACTED] should be stored protected from light.

[REDACTED] must be protected from light [REDACTED]

13.5 DOSES AND TREATMENT REGIMENS

13.5.1 Doses and treatment regimens group 1 to 4 (test products)

The test products (Immunose FLU, influenza antigen and saline, respectively) will be administered in 2 doses delivered at least 3 weeks apart. Up to 4 weeks between administrations is allowed.

A short instruction for nasal administration of Immunose FLU, influenza antigen and saline is provided below and a complete instruction is provided separately.

Prior to administration, the content of each vial should be mixed carefully. Upon administration, the subject should sit in an upright position and lean the head backwards (Figure 2 and Figure 3). A calibrated pipette and pipet tips must be used.

A total of 150 µl of IMP should be administered in each nostril. The nose drops must be applied on the upside nasal cavity.

Figure 2 Head position of subject upon nasal administration of test products (group 1 to 4)

Figure 3 Administration of test products (group 1 to 4)

13.5.2 Doses and treatment regimens group 5 and 6 (comparators)

The comparators ([REDACTED]) will be administered as a single dose according to the manufacturer's instructions.

[REDACTED] will be administered [REDACTED]

[REDACTED] will be administered [REDACTED]

13.6 INVESTIGATIONAL MEDICINAL PRODUCT ACCOUNTABILITY

It is the responsibility of the Investigator to establish a system for handling the IMPs, to ensure that:

- Deliveries of such products are correctly received and recorded by a designated person
- IMPs are handled and stored safely and properly
- IMPs are given only to study subject in accordance with the CSP
- All unused IMP and empty containers are stored until they have been checked by the monitor
- It is possible to reconcile records of all used and unused stocks as confirmed by Investigator's signature

The monitor(s) should collect any unused IMP from the sites and return the IMP to Eurocine Vaccines AB or representative when the dosing period is over.

13.7 METHOD OF ASSIGNING SUBJECTS TO TREATMENT GROUPS

13.7.1 Randomisation

At visit 2, subjects will be consecutively allocated to the 6 treatment groups in a 2:2:2:1:1:1 ratio. Group 1 to 3 will consist of 36 subjects and group 4 to 6 will consist of 18 subjects. The randomisation will be stratified by site and for each stratum an appropriate block size will be used to ensure the ratios between treatment groups.

Randomisation codes will be provided by PCG Clinical Services AB to [REDACTED].

13.8 ASSESSMENT OF TREATMENT COMPLIANCE

Following administration, the site personnel should evaluate whether the administration was successful or not (Y/N). Dripping, sneezing and swallowing in association with the administration must be commented on in the eCRF.

13.9 CONTINUATION OF MEDICATION AFTER THE STUDY

No subject will be offered continued treatment with any test product at the end of their study participation.

13.10 BLINDING

Treatments for group 1 to 4 will as far as possible be handled in a double blinded fashion. The influenza antigen without Endocine, and Immunose FLU with Endocine in different concentrations (1% and 2%, group 1 and 2, respectively) are slightly turbid to turbid liquids and is hence different from saline, which is clear and more transparent.

To maintain the blind, all test products (Immunose FLU with 1% and 2% Endocine, influenza antigen without Endocine and saline) will be provided in amber coloured bottles. The administration of the products will be carried out using coloured, yet transparent, pipet tips to partially mask the appearance of the test products but to allow for inspection of the volume prior to administration.

There is a risk that the person who administers the test products will be unblinded. Therefore, this person will not be involved in any study related evaluations. An independent evaluator will assess local tolerability reactions pre and post administration.

The comparators, [REDACTED] and [REDACTED] will be administered in an open label fashion [REDACTED].

13.10.1 Breaking the treatment code (unblinding)

Treatment code envelopes will be provided for each randomised subject. The code envelopes should be kept in a secure place with limited access. In case of emergency where it is crucial for the Investigator, or any other treating physician, to know which treatment has been given to the subject, the code envelope may be opened. If the code is broken, this must be documented on the treatment code envelope and in the subject's hospital records with date and name of the Investigator who decided to break the code.

In the event of an SAE, the Investigator may only break the treatment code if the appropriate future management of the subject necessitates knowledge of the current treatment. When an SAE may be a serious adverse drug reaction (SADR), the procedures for potential expedited reporting must be followed (Section 15.3.10).

14. STUDY ASSESSMENTS

The timing and frequency of the study visits are presented in Figure 1 and in the overall schedule of events for group 1 to 4 (Table 1) and group 5 and 6 (Table 3), respectively. A more detailed description for the timing of assessments is provided in Table 2 and Table 4 for group 1 to 4 and group 5 and 6, respectively.

14.1 STUDY VISITS

14.1.1 Visit 1, Screening

After written informed consent has been obtained, the following activities and assessments will be performed:

- Evaluation of eligibility criteria.
- Collection of demographic data.
- Recording of medical history.
- Physical examination.
- Recording of vital signs (heart rate and blood pressure).
- Recording of weight and height.
- 12-lead ECG.
- Pregnancy test, urine dipstick.
- Blood sample for viral screen (HIV, hepatitis B and hepatitis C).
- Urine drug screen (dipstick).
- Urine sampling for assessment of urinalysis parameters.
- Blood sampling for assessment of haematology and clinical chemistry parameters. Fasting is not required.
- Nasal swab for nasal IgA analysis (pre-treatment sample, to be stored and analysed with the other immune samples. Performed at screening to save time at visit 2 especially for group 1 to 4).
- Recording of prior and concomitant medication.

Eligible subjects will be scheduled for Visit 2.

14.1.2 Visit 2

Subjects will arrive at the study clinic on Day 0. A re-assessment of eligibility will be made, see Section 12.6. Eligible subjects will be randomised to one of 6 treatment groups as detailed in Section 11 and 13.1.

The activities and assessments to be performed at Visit 2 are outlined below. For details on the timing of each assessment, refer to Table 2 (group 1 to 4) and Table 4 (group 5 and 6).

The following activities and assessments will be performed **before randomisation**:

- Pregnancy test (urine dipstick).
- Recording of vital signs (heart rate, blood pressure and body temperature).
- Recording of concomitant medication.
- Collection of pre-dose events.

The following activities and assessments will be performed **after randomisation** but **pre-dose**:

- Blood sampling for immunology analyses.

- Inspection of nasal cavities and recording of local tolerability parameters (group 1 to 4 and group 6).
- Inspection of administration site (upper arm) and recording of local tolerability parameters (group 5).

The **study drug administration** will be performed as summarized in Section 13.5.1 and Section 13.5.2 and according to the manufacturers' instructions as applicable.

The following activities and assessments will be performed **post-dose**:

- Recording of local tolerability parameters at 15 and 120 minutes post study drug administration.
- Recording of vital signs at 30 minutes and approximately 120 minutes post study drug administration (before the subject leaves the clinic).
- AE collection.
- Diary instructions for daily AE recording during 10 days starting in the evening the day after treatment.

14.1.3 Visit 3

The activities and assessments to be performed at Visit 3 are outlined below. A re-assessment of eligibility will be made prior to dosing, see Section 12.6. For details on the timing of each assessment, refer to Table 1, Table 2 and Table 3.

14.1.3.1 Visit 3 group 1 to 4

The following activities and assessments will be performed **pre-dose**:

- Pregnancy test (females only, urine dipstick).
- Review of diary since the previous visit.
- AE collection.
- Recording of concomitant medication.
- Recording of vital signs (heart rate, blood pressure and body temperature).
- Nasal swab for nasal IgA sampling (at least 60 minutes before assessment of the pre-dose assessment of local tolerability).
- Blood sampling for immunology analyses.
- Inspection of nasal cavities and recording of local tolerability parameters.

Nasal **study drug administration** will be performed as summarized in Section 13.5.1.

The following activities and assessments will be performed **post-dose**:

- Recording of local tolerability parameters at 15 and 120 minutes post study drug administration.
- Recording of vital signs at 30 minutes and approximately 120 minutes post study drug administration.
- AE collection.
- Diary instructions for daily AE recording during 10 days starting in the evening the day after treatment.

14.1.3.2 Visit 3 group 5 and 6

The following activities and assessments will be performed:

- Review of diary since the previous visit.

- AE collection.
- Recording of concomitant medication.
- Recording of vital signs (heart rate and blood pressure).
- 12-lead ECG.
- Physical examination.
- Urine sampling of urinalysis parameters.
- Blood sampling for assessment of haematology and clinical chemistry parameters. Fasting is not required.
- Nasal swab for nasal IgA analysis.
- Blood sampling for immunology analyses.

